4.0 Treatment Plan

4.1 Study Treatment

Patients will be treated with SGI-110 60mg/m² subcutaneously daily x 5 every 4 weeks until treatment failure or for a maximum of 2 years. Further therapy beyond 2 years could be extended if judged in the best patient interest. Treatment will be continued unless patients exhibit evidence of treatment failure, disease progression, experience an unacceptable toxicity, or the investigator determines that discontinuation of treatment is in the patient best interest.

All patients will be registered and entered through the Protocol Data Management System (PDMS).

4.2 Treatment Plan

- SGI-110 60mg/m² SQ daily x 5 days every 4 weeks for a total of 24 courses. Interval between courses can be extended to 8 weeks depending on toxicities, patient condition, and recovery of course.
- Patients should not be taken off therapy with SGI-110 prior to completion of the first 3 courses unless for unequivocal disease progression while on therapy, unacceptable toxicities, or patient request.
- Patients with stable disease after completion of three courses can continue for up to 6 courses. Unless patients have achieved at least a hematological improvement after 6 courses, they should then be taken off therapy with SGI-110.

- Patients may receive up to 24 courses depending on response and tolerability of therapy. Courses should be repeated every 4 to 8 weeks. Continuing of SGI-110 beyond 24 courses is an option if judged to be in the patient best interest.

4.2.1 Supportive Measures during Treatment

Necessary supportive measures for optimal medical care are to be given throughout the study as indicated by the treating physician's assessment of the patient's medical need and by the institutional guidelines as far as established.

4.3 Dose Modifications

4.3.1 Induction, Re-Induction, and Consolidation Cycles

All dose delays, reductions, and modifications for hematologic and non-hematologic toxicities will be assessed according to Section 9, and Table 5 and 6.

4.3.2 Hematologic (Blood/Bone Marrow) Toxicity

No dose reductions, delays, or modifications are required for hematologic toxicities during the first 2 cycles of treatment. It is assumed that low counts at diagnosis are due to involvement by the disease process and require therapy for improvement.

Patients who achieve a CR that have not recovered peripheral blood counts will be treated with subsequent cycles and other dose modifications implemented at the discretion of the investigator.

4.3.3 Non-Hematologic Toxicity

- Reduce SGI-110 by 25% for grade 3-4 reversible toxicities (same as above). Dose reduction for grade 2 reversible toxicities and other dose modifications can be implemented if in the best interest of the patient, after discussion with primary investigator.

4.4 Infection Prophylaxis

The use of prophylactic antibacterial (e.g., levaquin), antifungals (e.g., voriconazole), and antiviral agents (e.g., valacyclovir) is recommended according to institutional guidelines as established.

4.4.1 Colony Stimulating Factors

Hematopoietic growth factors (e.g., granulocyte colony stimulating factor [G-CSF], (erythropoietin) can be administered at the treating physician's discretion and judgment.

4.4.2 Concomitant Therapy

No concomitant cytotoxic therapy or investigational therapy is allowed during the study. Concomitant medications will be documented in the medical record.

5.0 Pretreatment Evaluations

History and physical, CBC with differential and platelets, chemistry profile (total bilirubin, serum creatinine, SGPT or SGOT, uric acid, LDH, potassium, magnesium) within 14 days of therapy start.

Bone marrow aspirate and/or biopsy within 28 days of therapy start. The bone marrow evaluation will include immunophenotyping by flow cytometry and cytogenetic studies.

Pregnancy (urine or blood) test for women of childbearing potential within two weeks prior of entering this study. Child bearing potential is defined as not post-menopausal for 12 months or no previous surgical sterilization.

Screening physical assessment does not need to be repeated on Cycle 1 Day 1, if performed within 2 days.

6.0 Evaluation during Study

- CBC with differential and platelet counts weekly in the first course, then every 2 to 8 weeks thereafter as long as on study. No differential is needed if the WBC is $< 1.0 \times 10^9/L$.
- Chemistry profile (at least creatinine, SGOT or SGPT, total bilirubin) every 2-8 weeks while on therapy, then every 8 to 12 weeks as long as on study.
- Bone marrow aspirate and/or biopsy at the end of course 1 and/or 2 of SGI-110 (day 28 +/- 7 days). If a patient is not in remission at this point, further bone marrow aspirate and/or biopsy should be scheduled to document remission, for example at the end of course 6 (day 28 +/- 7 days).
- Bone marrow tests can be ordered more frequently if mandated by development of peripheral blood counts. No repeat bone marrow is necessary if non-response or progressive disease can be unequivocally diagnosed from peripheral blood tests or, in patients with a WBC ≤ 0.3 if the bone marrow test is considered non-contributory by the investigator at any time point.
- Follow up marrow tests should include cytogenetic analysis for those patients who had abnormalities prior to therapy start.
- Repeat physical examination (problem focused) on Day 1 (± 3 days) of every cycle as long as on active therapy.
- After completion of therapy and/or 30 days after last dose of study drug, patients will be observed for survival only when off active treatment. Patients will be called 30 days after last dose of study drug and every 2 months ($+- 2$ months) thereafter.
- Optional: Blood 10cc pretreatment and on Day 5 $+- 2$ days and Day 14 $+- 2$ days to evaluate effect of SGI-110.
- All outside labs will need to be reviewed, signed and dated by the Principal Investigator (PI) or treating physician (listed on the Delegation of Authority) prior to submission to the electronic medical record. The PI or treating physician should appraise abnormal lab results and determine/document clinical significance

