1.0 Objectives

Primary objective:

1. To evaluate the complete response (CR) rate with SGI-110 in patients with higher risk myelodysplastic syndrome (MDS).

Secondary objectives:

1. Overall response rate, survival, transformation to AML, transfusion independence
2. Safety and toxicity

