2.4 Rationale for Proposed Schedule

The best approach for patients with higher-risk MDS remains to be defined. Both azacitidine and decitabine by themselves have low objective response rates, and a modest and limited survival benefit. From the early phase 1-2 experiences with SGI-110, it appears to be potentially more effective and perhaps safer than azacitidine and decitabine. We would like to expand our institutional experience with SGI-110 in newly diagnosed higher risk MDS to define more precisely the rates of CR, overall response, duration of response, survival and toxicity profiles. We will also assess determinants of better outcome with SGI-110 in MDS. The schedule chosen is based on the Phase II expansion of SGI-110 in higher risk MDS which treated a limited number of 40 patients. We will use SGI-110 60mg/m² subcutaneously daily x 5 every 4 weeks. We would like to gain experience on the efficacy, outcome and safety in 100 patients with newly diagnosed MDS. The primary endpoint of the study is the objective CR rate. Secondary endpoints are overall response rate, rates of survival and transformation to AML, and toxicity profile.

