The number of patients evaluated for mortality	5	10	15	20	25	30	35	40	45	50	55	60	65	70	75	80	85	90	95
The number of patients dead is greater than or equal to	3	4	5	5	6	7	8	8	9	10	10	11	12	12	13	14	14	15	15

Table 8. Operating characteristics for mortality monitoring

True Mortality Rate	Early Stopping Probability	Sample Size		
		25 th percentile	Median	75 th percentile
0.06	0.0111	100	100	100
0.08	0.0444	100	100	100
0.10	0.1291	100	100	100
0.12	0.2751	85	100	100
0.14	0.4759	40	100	100

Statistical Analysis Plan

All patients who received at least 1 dose of the experimental treatment will be included in the intent-to-treat analysis for efficacy and safety. Safety data will be summarized using frequency and percentage, by organ type, grade and attribution. Complete response and overall response rates will be estimated along with the 95% credible intervals. Survival times (overall survival, time to AML transformation and event-free survival) will be estimated using the Kaplan-Meier method for each patient cohort.

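### Follow-up off treatment is limited to survival, so AML that develops after stopping need not be recorded, and the planned time-to-AML estimate may be biased in a direction the plan leaves open

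*Combined protocol and SAP*

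**What the plan says.** Section 1.0 lists among the secondary objectives "Overall response rate, survival, transformation to AML, transfusion independence". Section 2.4 repeats it: "Secondary endpoints are overall response rate, rates of survival and transformation to AML, and toxicity profile". The Statistical Analysis Plan paragraph in section 9.0 states "Survival times (overall survival, time to AML transformation and event-free survival) will be estimated using the Kaplan-Meier method", and its analysis set is all patients with at least one dose, so early leavers are included. That paragraph gives no definition of the AML event, no censoring rule and no handling of death without AML.

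On follow-up after treatment, section 6.0 says "patients will be observed for survival only when off active treatment". Contact is by telephone at 30 days after the last dose and about every 2 months thereafter.

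Treatment ends for reasons related to outcome. Section 4.1 treats "until treatment failure or for a maximum of 2 years". Section 4.2 adds "Unless patients have achieved at least a hematological improvement after 6 courses, they should then be taken off therapy with SGI-110". Section 8.0 lists progressive disease among the reasons for leaving the study. On timing, section 4.2 says "Courses should be repeated every 4 to 8 weeks".

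Two other provisions come close. The blood-count line in section 6.0 runs "every 2 to 8 weeks thereafter as long as on study", and the chemistry line there also continues while the patient is on study. Section 10.0 captures serious adverse events to 30 days after the last dose and, after that, only those related to treatment.

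**The concern.** The endpoint outlasts the data collection written for it. AML that itself prompts stopping will be seen. AML that appears in a patient already off drug does not have to be recorded anywhere in the text. Patients without improvement after 6 courses lose AML observation at that point, while patients who improve remain under assessment for as long as they are treated. Observation time therefore depends on response, and response is plausibly related to the risk of AML.

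At stake is whether the reported time-to-AML curve describes the treated patients. If leavers are kept in the risk set as AML-free, unseen events push the estimated AML rate down. If they are censored at stopping, the estimate falls only if AML risk is higher after stopping, and it can rise if risk is lower. If deaths are also censored, Kaplan-Meier overstates the proportion who actually transform. A reader of the final report could not tell which of these effects dominates.

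**Working it through.** The plan states no event count, rate or precision for time to AML, so there is no figure to reproduce. What follows is an illustration of size.

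**Inputs from the documents.** Courses last 4 to 8 weeks, with a decision after 6 courses and up to 24 courses (section 4.2). Six courses take 6 × 28 = 168 days, about 5.5 months, or 6 × 56 = 336 days, about 11.0 months. Twenty-four courses take about 22.1 or 44.2 months.

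**Assumed inputs (not in the documents).** A fraction f = 0.40 are leavers, who stop after 6 courses if still alive and AML-free. AML hazard is 0.05 per month in leavers and 0.015 in stayers. Death without AML is 0.03 per month in both. AML before exit counts as recorded. Stayers are taken as observed to 24 months.

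**Formula.** The cumulative incidence of AML by time t, with AML hazard h and death hazard d, is CI = h/(h+d) × (1 − exp(−(h+d)t)).

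- Leavers, 24 months: 0.05/0.08 × (1 − exp(−1.92)) = 0.5334
- Stayers, 24 months: 0.015/0.045 × (1 − exp(−1.08)) = 0.2201
- All: 0.4 × 0.5334 + 0.6 × 0.2201 = 0.345, or 34.5 per 100
- Leavers up to exit: 0.2225 at 5.5 months, 0.3658 at 11 months
- Unrecorded: 0.4 × (0.5334 − 0.2225) = 0.124, or 0.4 × (0.5334 − 0.3658) = 0.067

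So 12.4 or 6.7 per 100 are missed, which is 36% or 19% of all transformations.

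**Scaling to a figure in the documents.** Section 2.2 gives a median of 21 months to leukemic transformation or death on azacitidine. In the model above that median solves 0.4·exp(−0.08t) + 0.6·exp(−0.045t) = 0.5, giving t = 12.1 months. Multiplying every hazard by 12.1/21 = 0.576 gives 26.0 transformations per 100. Of these, 0.4 × (0.4183 − 0.1400) = 11.1 or 0.4 × (0.4183 − 0.2486) = 6.8 per 100 are missed, a share of 43% or 26%.

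**Direction of the Kaplan-Meier estimate at 24 months, if deaths are censored** (the plan does not say they are; paired values are exit at 5.5 and 11 months):

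| Hazards | Modelled incidence | Full follow-up | Leavers censored at exit | Leavers carried AML-free |
|---|---|---|---|---|
| Base case | 34.5% | 46.1% | 35.1%, 39.2% | 27.8%, 35.1% |
| Scaled to 21 months | 26.0% | 31.2% | 22.1%, 25.2% | 17.1%, 22.1% |
| Equal AML hazard, 0.015 | 22.0% | 30.2% | 30.2%, 30.2% | 21.3%, 24.2% |

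Kaplan-Meier here is 1 − exp(−integral of the observed AML hazard). With equal hazards, censoring at exit adds no bias beyond the treatment of death. With the leaver hazard reduced to 0.0075 and exit at 5.5 months, censoring raises the estimate from 24.7% (full follow-up) to 29.1%.

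**A differently built illustration.** Here stopping occurs throughout treatment (mean 5 to 12 months), AML is seen to one month after the last dose, and AML hazards off treatment range from half to three times those on treatment. The missed share is 37% to 76%. Censoring leavers gives from 29.6% against a true 30.0% to 42.8% against 21.8%. Keeping them in the risk set is always too low, for example 9.4% against 31.7%. For AML or death as a composite, with deaths followed, the 24-month event proportion falls from 78–85% with full capture to 71–73%.

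**The case against.** **The laboratory lines.** Blood counts continue while on study, and the chemistry line separates time on therapy from time on study, so some laboratory follow-up off therapy seems intended. Section 6.0 also accepts that progression can sometimes be diagnosed from blood alone and routes outside results into the medical record. This stands as an inconsistency with the survival-only sentence. It does not close the gap: none of these lines asks for AML status or a date, and the laboratory schedule ends when a patient is taken off study.

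**Case report forms.** Section 10.0 refers to protocol-specific data fields and an appendix on leukemia event recording that are not in the text available. A reader might infer that AML after stopping will never be recorded. The documents do not support that. They show only that recording is not required, and charts may show some cases.

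**The endpoint may be a composite.** Section 2.2 reports time to leukemic transformation or death for azacitidine. If that is meant here, the competing-risk argument falls away. The follow-up gap remains, because an unseen AML moves the event to the later date of death or leaves the patient counted as event-free.

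**Direction and size.** A reader might infer that AML will be understated, or that Kaplan-Meier will usually overstate it. Neither follows, since the sign changes with the hazards and with the rule. Nor is the figure bound to be far off: the base case with leavers censored at 5.5 months gives 35.1% against 34.5%, because two errors happen to cancel.

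**Consequence.** No hypothesis, sample size or decision depends on this endpoint. That is correct and limits the weight of the point.

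**Conclusion.** The point holds in this form: the protocol does not require AML status or a date after treatment stops, stopping is tied to prognosis, and the planned time-to-AML estimate may be biased in a direction set by choices the plan leaves unstated. The illustration puts the unrecorded events at about 12 or 7 of 34.5 transformations per 100 patients by 24 months. Scaled to the 21-month median in section 2.2, the missed share is 43% or 26%. Every hazard and the 40% leaving are assumptions, and the azacitidine trial behind that median was not confined to advanced disease (67% by FAB). The numbers show that the loss could be material; they do not predict its size. This is a descriptive secondary endpoint that should be fixed. CR, overall survival and the stopping rules are unaffected.

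**What to change.** In section 6.0, change the survival-only limit to survival and AML transformation (yes/no and date). Collect this at the 30-day and 2-monthly calls already scheduled and from the chart. When a death is reported, ask whether AML had been documented before it. State whether the laboratory lines that run while on study apply after therapy ends, so that they agree with this sentence.

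In the Statistical Analysis Plan paragraph of section 9.0:

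- State whether the endpoint is AML alone or AML or death, and define the AML event.
- Censor living, AML-free patients at the last contact with known AML status, not at the end of treatment.
- If the endpoint is AML alone, report cumulative incidence with death without AML as a competing event.

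The cost is two data fields on existing calls, some chart review and a few lines of text, with no new visits or procedures. The downside is that dates reported by phone are less precise.

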7.0 Criteria for Response

1) Complete Remission:

Normalization of the peripheral blood and bone marrow with $\leq 5\%$ bone marrow blasts, a peripheral blood granulocyte count $\geq 1.0 \times 10^9/L$, and a platelet count $\geq 100 \times 10^9/L$. Hgb $\geq 11 \text{ g/dL}$ at any point while on treatment after the first cycle of therapy.

Addition of CRI (Complete Remission without blood count recovery) = Peripheral blood and bone marrow counts as per CR, but with platelet counts $30-100 \times 10^9/L$ and/or ANC $< 1.0 \times 10^9/L$.

2) Partial Remission:

Patients must demonstrate all CR criteria if abnormal before treatment except that marrow blasts should decrease by 50% or more compared to pretreatment levels or may demonstrate a less-advanced MDS disease classification category than prior to treatment.

3) Hematologic Improvement:

Response maintained for at least 8 weeks:

- Hemoglobin (pretreatment $< 11 \text{ g/dL}$): improves by 1.5 g/dL or reduced by 4 units of RBC transfusions in 8 week time period compared with pretreatment transfusion number in 8 weeks. Only RBC transfusion given for Hgb of $\leq 9.0 \text{ g/dL}$ will count in the RBC transfusion response evaluation.
- Platelet (pretreatment $< 100 \times 10^9/L$): absolute increase of $\geq 30 \times 10^9/L$ for patients starting with plt $> 20 \times 10^9/L$ OR increase from $< 20 \times 10^9/L$ to $> 20 \times 10^9/L$ and by at least 100%.
- Neutrophil (pretreatment $< 1 \times 10^9/L$): increase 100% and absolute increase $> 0.5 \times 10^9/L$

4) Clinical Benefit:

Platelets increase by 50% and to above $30 \times 10^9/L$ untransfused (if lower than that pre-therapy); or granulocytes increase by 100% and to above $1 \times 10^9/L$ (if lower than that pre-therapy); or hemoglobin increase by 2 g/dL ; or transfusion independent; or splenomegaly reduction by $\geq 50\%$; or monocytosis reduction by $\geq 50\%$ if pretreatment $> 5 \times 10^9/L$.

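### Transfusion independence, a secondary objective, has as its only criterion a state with no baseline condition, so a patient never transfused can meet it without any change

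*Combined protocol and SAP*

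**What the plan says.** Section 1.0 gives the first secondary objective as "Overall response rate, survival, transformation to AML, transfusion independence". Section 2.4 restates the endpoints without the last of these: "Secondary endpoints are overall response rate, rates of survival and transformation to AML, and toxicity profile".

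Section 7.0 is the only place with criterion text. Item 4, Clinical Benefit, offers six alternatives, one of which is "or transfusion independent". Nothing attached to those words gives a pretreatment requirement, a transfusion-free period, or the blood component meant. In the same item, the platelet and granulocyte alternatives each carry the condition "if lower than that pre-therapy", and the monocytosis alternative has a pretreatment threshold.

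Item 3, Hematologic Improvement, is separate. It requires "Response maintained for at least 8 weeks", and its red-cell transfusion route is "reduced by 4 units of RBC transfusions in 8 week time period compared with pretreatment transfusion number in 8 weeks".

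On analysis, Section 9.0 says "All patients who received at least 1 dose of the experimental treatment will be included in the intent-to-treat analysis for efficacy and safety" and "Complete response and overall response rates will be estimated along with the 95% credible intervals". It names no analysis of transfusion independence and no subset defined by transfusion need at entry.

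**The concern.** An objective of this kind is meant to show that patients who needed transfusions stopped needing them. The criterion as worded asks only whether the patient is independent. Eligibility in Section 3.0 rests on IPSS risk group or blast percentage and does not require transfusion dependence, so patients already independent can enter.

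If independence is then counted over all treated patients, the result mixes two groups: those who became independent and those who always were. With one arm, no comparator shares the same mix, so a reader cannot tell how much of the figure is drug effect. The figure would also be hard to set beside another series with a different share of transfused patients at entry.

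**Working it through.** The documents state no figure for this endpoint, so there is none to reproduce. The check has two parts: a comparison of the texts, and an illustration of size.

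**1. The six Clinical Benefit alternatives (Section 7.0, item 4)**

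| Alternative | Worded as | Pretreatment condition |
|---|---|---|
| Platelets | increase | yes |
| Granulocytes | increase | yes |
| Hemoglobin | increase | none |
| Transfusion independence | state | none |
| Splenomegaly | reduction | none |
| Monocytosis | reduction | yes |

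Hemoglobin and splenomegaly have no threshold but still require a change, so an unchanged patient cannot meet them. Transfusion independence is the only alternative that an unchanged patient can meet.

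**2. Whether Hematologic Improvement fills the gap**

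It does not, because it measures a reduction of 4 units over 8 weeks. A patient going from 10 units to 6 has a reduction of 10 − 6 = 4 and qualifies, but is not independent. A patient going from 2 units to 0 is independent, but the reduction of 2 falls short of 4.

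**3. Whether another section supplies the condition**

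Section 3.0 has no transfusion criterion. Sections 5.0 and 6.0 list no transfusion history or on-study transfusion record. Section 9.0 analyses all treated patients.

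**4. Illustration of size**

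The maximum N is 100 (Section 9.0). The following are assumptions; the documents give none of them:

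- f = share independent at entry
- r = share of those who stay independent
- c = share of patients dependent at entry who become independent

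Formulas:

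- As written, over all treated patients: N × [f × r + (1 − f) × c]
- Restricted to patients dependent at entry: N × (1 − f) × c out of N × (1 − f)

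With no drug effect (c = 0) the first reduces to N × f × r:

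| f | As written, r = 80% | As written, r = 100% | Restricted |
|---|---|---|---|
| 20% | 16/100 | 20/100 | 0/80 |
| 40% | 32/100 | 40/100 | 0/60 |
| 60% | 48/100 | 60/100 | 0/40 |

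With c = 20% and r = 100%:

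| f | As written | Restricted |
|---|---|---|
| 20% | 20 + 16 = 36/100 | 16/80 = 20% |
| 40% | 40 + 12 = 52/100 | 12/60 = 20% |
| 60% | 60 + 8 = 68/100 | 8/40 = 20% |

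The same conversion rate gives 36% to 68% under the wording as it stands, depending only on who was enrolled. The restricted rate stays at 20%.

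**The case against.** The strongest reply is that the wording is ambiguous rather than wrong. The phrase sits under response criteria, among five items that all describe improvement, and a sensible assessor could take it to mean becoming independent. That reading is open, but the text does not state it, and the same sentence spells out baseline conditions for three of its other items. Two assessors could therefore classify the same untransfused patient differently.

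Four stronger inferences are tempting, and the documents do not support them.

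- **A reader might infer that the overall response rate is inflated.** No section says that Clinical Benefit counts toward overall response, so this is possible but not established. The rule in Section 4.2 for continuing after 6 courses turns on hematological improvement, which has its own baseline thresholds and duration.
- **A reader might infer that a planned secondary endpoint rate is biased.** Section 2.4 leaves transfusion independence off the endpoint list, Section 9.0 plans no rate for it, and nothing says that the Clinical Benefit item defines the objective. What can be said is that it is the only criterion text available if a rate is reported.
- **A reader might infer that the missing duration is peculiar to this item.** No Clinical Benefit alternative carries a duration. The point specific to this item is the missing baseline condition. A duration is needed because independence is a named objective.
- **A reader might take the percentages as estimates.** They are assumed inputs carried through a formula. Full retention (r = 100%) is the extreme case: Section 2.3.4 lists anemia and thrombocytopenia among the drug's common risks, so some patients independent at entry may need transfusions later.

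**Conclusion.** The point holds in a limited form. Followed as written, the only criterion for transfusion independence credits a patient who was not transfused before treatment and has not changed. A rate over all treated patients would partly measure baseline mix. The contribution with no drug effect is f × r, or 16% to 60% of patients for f between 20% and 60% and r between 80% and 100%. That range rests entirely on assumed values of f and r, and the documents support no particular figure.

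The primary complete response endpoint and the futility, toxicity and mortality rules do not use this criterion and are unaffected. The matter should be corrected before any transfusion-independence result is reported, but it does not threaten the trial's main conclusion.

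**What to change.** 1. In Section 7.0, add to the Clinical Benefit item a condition such as *(if transfusion dependent pre-therapy)*, parallel to the platelet and granulocyte items.
2. In Section 9.0, define the rate for the objective. The numerator is patients free of transfusion for at least 8 consecutive weeks, which is the duration the protocol already uses for Hematologic Improvement. The denominator is treated patients who were transfused in the 8 weeks before treatment.
3. State whether red-cell transfusions, platelet transfusions or both count, in the baseline definition and in the outcome. The Hematologic Improvement rule covers only red cells, and only those given at a hemoglobin of 9.0 g/dL or below, so it cannot simply be borrowed.
4. Add transfusion recording to Sections 5.0 (the preceding 8 weeks) and 6.0 (on study).
5. Align Sections 1.0 and 2.4 on whether transfusion independence is a secondary endpoint.

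The cost is a few sentences, a little more data recording, and a smaller denominator. At a true rate of 20%, the standard error √(0.2 × 0.8 / n) is 4.0 percentage points with n = 100. It is 4.5 with n = 80, 5.2 with n = 60 and 6.3 with n = 40. That loss of precision is acceptable for a rate that reflects change on treatment.
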